4.6.2.1.8. Peripheral Edema

Peripheral edema will be searched by MedDRA PTs (see Section 6.8) from all TEAEs. The number and percentage of participants experiencing treatment-emergent peripheral edema will be summarized by PT.

4.6.2.1.9. Hypokalemia

The TEAEs of hypokalemia will be identified by narrow terms in the *Hypokalaemia* SMQ (20000233). A summary of the number of participants with treatment-emergent events meeting the SMQ narrow search criteria by PT will be provided.

4.6.2.1.10. Hyperglycemia

Study treatments were designed as treatments for hyperglycemia in patients with diabetes. Therefore, hyperglycemia is usually not reported as an AE in diabetes studies. However, if a participant develops severe, persistent hyperglycemia after randomization, rescue therapy will be considered. A listing of participants who receive rescue medication will be provided.

4.6.2.1.11. Major Adverse Cardiovascular Events

Potential cerebrocardiovascular events will be identified by the investigative site or by a medical review conducted by the sponsor or designee. A blinded, external Clinical Events Committee will adjudicate the events in a consistent and unbiased manner. Events include

- death
- cardiac ischemic events (including myocardial infarction or *hospitalization for unstable angina*)
- cerebrovascular events (including stroke or transient ischemic attack)
- hospitalization for unstable angina
- hospitalization for heart failure, and
- coronary revascularization procedure.

Only major adverse cardiovascular events (MACE) confirmed by the adjudication committee will be considered as AEs of special interest. A listing of MACE reported by the investigator, including the reported term and adjudication results, will be provided.

4.6.2.1.12. Medication Errors of Interest

Medication Errors of Interest (MEI) are defined as medication error AEs (SMQ 20000224 - narrow and broad terms) that meet the criteria of important protocol deviation (IPD) indicative of multiple doses, according to the Trial Issue Management Plan. These events are considered IPDs because of their potential to impact participants' safety. For this same reason, these events are considered of special interest among all medication error AEs reported in the trial's CRF.

MEI AEs are categorized as IPDs of "Investigational Medicinal Product and/or Investigational Device." Screening and identification of MEI AEs will occur during routine review of the protocol deviations and trial level safety reviews.

The number and percentage of participants reported with MEI will be analyzed.

A listing of MEI will be provided. The listing will indicate if severe hypoglycemia or P-R hypoglycemia occurred after the MEI.

4.6.3. Additional Safety Assessments

4.6.3.1. Hypoglycemic Events

4.6.3.1.1. *Participant-Reported Hypoglycemic Events*

Hypoglycemia events will be derived in the analysis datasets and documented as Level 1, Level 2, and Level 3 (severe hypoglycemia), according to definitions based on the American Diabetes Association criteria:

- Level 1 - Glucose <70 mg/dL (3.9 mmol/L) and ≥ 54 mg/dL (3.0 mmol/L).
- Level 2 - Glucose <54 mg/dL (3.0 mmol/L).
- Level 3 - Severe hypoglycemia (confirmed by the investigator to be an event that required assistance for treatment).

The Level 2 and Level 3 events are considered as clinically significant hypoglycemia. Therefore, the analysis on a composite of Level 2 and Level 3 (denoted as Level 2/3) hypoglycemia will also be conducted.

The hypoglycemia will also be further classified into

- nocturnal hypoglycemia (occurs between midnight and 0600), and
- non-nocturnal hypoglycemia (occurs between 0600 and midnight).

If a hypoglycemic event is within 60 minutes of another one hypoglycemic event, it is considered as a continuation of the previous event. If there are multiple hypoglycemic events within 60 minutes of each other, then all events will be combined into a single event, which has the

- earliest date time
- minimum glucose value, if applicable
- maximum severity (Level 1, 2 or 3)
- combined symptoms and outcomes, and
- time of nocturnal if any of the events is nocturnal

of the multiple hypoglycemic events.

The combined event starts from the first record with Level 1, 2 or 3, and ends when there are no more events for at least 60 minutes.

The evaluation of potential persistent/recurrent hypoglycemia events will be through assessment of the events confirmed by investigators based on clinical judgment and through events identified by a prespecified criteria (see Section 4.6.2.1.2 and Appendix 9 [Section 6.9] for details) using information based on participant-reported hypoglycemia.

The details of planned analyses are provided in the following table.

Endpoint	Analysis Period ^a	Statistical Method
Event rate of Level 1 hypoglycemia events (events/participant/year) • all documented	Baseline, Weeks 0-6, 0-12, 0-26, 0-52, 12-26, 26-52, and the posttreatment period	Negative binomial regression with treatment, baseline HbA1c, and baseline Level 1 hypoglycemia rate as covariates and log (exposure/365.25 days) as the offset in the model
Event rate of Level 2 hypoglycemia events (events/participant/year) • all documented	Baseline, Weeks 0-6, 0-12, 0-26, 0-52, 12-26, 26-52, and the posttreatment period	Negative binomial regression with treatment, baseline HbA1c, and baseline Level 2 hypoglycemia rate as covariates and log (exposure/365.25 days) as the offset in the model
Event rate of Level 3 hypoglycemia events (events/participant/100 years) • all documented	Baseline, Weeks 0-26, 0-52, 26-52, and the posttreatment period	Negative binomial regression with treatment and baseline HbA1c, and baseline Level 3 hypoglycemia rate as covariates and log (exposure/36525 days) as the offset in the model If the number of events is too small to run the negative binomial regression, the exposure-adjusted rate (calculated by total number of events divided by total exposure for individual participants) will be provided, and the empirical method (see Appendix 10 [Section 6.10] for details) will be used for treatment comparison.
Event rate of Level 2/3 hypoglycemia events (events/participant/year) • all documented • nocturnal, and • non-nocturnal	Baseline, Weeks 0-6, 0-12, 0-26, 0-52, 12-26, 26-52, and the posttreatment period	A negative binomial regression with treatment, baseline HbA1c, and baseline hypoglycemia rate of the same hypoglycemia type as covariates and log (exposure/365.25 days) as the offset in the model. The plots of the mean cumulative functions (MCFs) by each treatment arm will also be created. The population mean for cumulative number of events up to time t, M(t), will be estimated using a nonparametric estimation method described by Nelson ^b .
Incidence of Level 1 hypoglycemia events • all documented	Baseline, Weeks 0-6, 0-12, 0-26, 0-52, 12-26, 26-52, and the posttreatment period	Logistic regression with treatment, baseline HbA1c, and baseline Level 1 hypoglycemia incidence as covariates
Incidence of Level 2 hypoglycemia events • all documented	Baseline, Weeks 0-6, 0-12, 0-26, 0-52, 12-26, 26-52, and the posttreatment period	Logistic regression with treatment, baseline HbA1c, and baseline Level 2 hypoglycemia incidence as covariates
Incidence of Level 3 hypoglycemia events • all documented	Baseline, Weeks 0-26, 0-52, 26-52, and the posttreatment period	Logistic regression with treatment and baseline HbA1c as covariates

Endpoint	Analysis Period ^a	Statistical Method
Incidence of Level 2/3 hypoglycemia events 
 • all documented • nocturnal, and • non-nocturnal 	Baseline, Weeks 0-6, 0-12, 0-26, 0-52, 12-26, 26-52, and the posttreatment period	Logistic regression with treatment, baseline HbA1c, and baseline hypoglycemia incidence of the same hypoglycemia type as covariates.
Potential persistent-recurrent hypoglycemia events 
 • identified by investigators and • identified by a prespecified criteria (defined in Appendix 9 [Section 6.9]) 	Safety analysis period (see the definition in Section 4.6)	The number of participants with at least 1 event will be summarized and compared by Fisher's exact test. The number of events will also be provided. Listings of the events will also be provided.

Abbreviations: HbA1c = hemoglobin A1c; Level 2/3= Level 2 and Level 3 composite; mITT = modified intent-to-treat.

^a For analysis for baseline period, negative binomial regression or logistic regression will not include baseline HbA1c and baseline hypoglycemia for treatment companions.

b (Nelson 2003)

Note: The yearly hypoglycemia rate during the defined period is calculated by the number of hypoglycemic events within the period/number of days a participant is at risk within the period \times 365.25. For rare events, 100-year rate will be provided. The hypoglycemia incidence during the defined period indicates if the participant has at least 1 hypoglycemia event within the period (yes/no).

4.6.3.1.1.1. Sensitivity AnalysisError! No document variable supplied.

A sensitivity analysis will be done for selected hypoglycemic endpoints where all hypoglycemic events are considered 1 hypoglycemic episode until a succeeding glucose value is ≥ 70 mg/dL.

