6.6.1. Transitioning off of Study Basal Insulin

At the last treatment visit (Visit 29 [Week 52] or ET visit), the investigator will prescribe a non-study basal insulin for use during the safety follow-up period.

The investigator, in consultation with the participant, will decide on prandial insulin therapy for use during the safety follow-up period.

Study participants treated with LY3209590

Participants will administer their last dose of LY3209590 at Week 51 of the study and can begin the transition to the non-study insulins after Visit 29 (Week 52). At Visit 29 (Week 52), the investigator will review instructions for transitioning to the non-study insulins with the participant. The non-study daily basal insulin treatment should be started slowly and under regular review of glucose profiles after discontinuation of LY3209590.

Since LY3209590 has a half-life of approximately 17 days, a slow up-titration of the non-study daily basal insulin is necessary to prevent hypoglycemia due to overlapping insulin action. Non-study basal insulin would not be required until the study participant's fasting glucose is above 100 mg/dL (5.5 mmol/L), and then daily basal insulin would be initiated and adjusted based on fasting glucose, CGM profile, and hypoglycemia evaluation. The investigator should consider titration of the non-study basal insulin to reach 50% of the required daily basal insulin dose at approximately 2 weeks and 80% of the required daily basal insulin dose at approximately 4 weeks. An unscheduled visit in addition to Visit 801 may occur during this time to facilitate the transition to non-study daily basal insulin.

Study participants treated with insulin degludec

Participants assigned to the insulin degludec treatment arm will transition to their non-study basal insulin after Visit 29 (Week 52) with dose adjustment per investigator discretion based on fasting glucose, CGM profile, and hypoglycemia evaluation and in accordance with the local product label for the basal insulin.

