9.3. Statistical Analyses

9.3.1. General Considerations

Statistical analysis of this study will be the responsibility of Lilly or its designees.

Any change to the data analysis methods described in the protocol will require an amendment ONLY if it changes a principal feature of the protocol. Any other changes to the data analysis methods described in the protocol, and the justification for making the change, will be described in the SAP or the clinical study report. Additional exploratory analyses of data will be conducted as deemed appropriate.

Unless otherwise stated, the efficacy analyses will be conducted on either EAS1 or EAS2, and the safety analysis will be conducted on the SS. All tests of treatment effects using statistical models will be conducted at a 2-sided alpha level of 0.05 and 2-sided 95% CI will be provided.

Unless otherwise stated, the other secondary and tertiary efficacy measures will be analyzed on EAS2 using the data up to the discontinuation of LY3209590 or insulin degludec, defined by the date of last study dose +10 days or the initiation of rescue medication whichever is earlier.

Handling of missing, unused, and spurious data are addressed prospectively in the overall statistical methods described in the protocol and in the SAP, where appropriate. Adjustments to the planned analyses are described in the final CSR.

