4.9. Changes to Protocol-Planned Analyses

There are no changes but additional details are provided to the analyses described in the protocol.

5. Sample Size Determination

Approximately 670 participants will be randomized to LY3209590 and insulin degludec in a 1:1 ratio. With the assumption of 15% dropout at Week 26, approximately 284 and 284 participants will complete 26 weeks of treatment on LY3209590 and insulin degludec, respectively.

The primary objective of this study is to test the hypothesis that LY3209590 is noninferior to insulin degludec on glycemic control as measured by change from baseline to Visit 22 (Week 26) in HbA1c in participants with T1D currently basal-bolus insulin.

Assuming an NIM of 0.4%, no true difference between treatment groups, and an SD of 1.1%, 568 completers (284 on LY3209590 and 284 on insulin degludec) will provide at least 99% statistical power to show noninferiority between LY3209590 and insulin degludec using the upper limit of a 2-sided 95% CI (LY3209590 - insulin degludec). This sample size also has at least 90% statistical power to show noninferiority between LY3209590 and insulin degludec using a 0.3% NIM at Week 26.

The 568 completers will provide 90% statistical power to demonstrate the superiority (LY3209590 vs insulin degludec) of change in HbA1c from baseline to 26 weeks (assuming an SD of 1.1% and true mean difference of -0.3%) using the α of 0.05.

The 568 completers will provide at least 99% statistical power to show the superiority of the percentage of time in glucose range between 70 and 180 mg/dL (3.9 and 10.0 mmol/L), inclusive, measured by CGM 4 weeks prior to Week 26 between LY3209590 and insulin degludec (assuming an SD of 10% and true mean difference of 5%) using the α of 0.05.

The 568 completers will provide 80% statistical power to show the superiority of the event rate of clinically significant nocturnal hypoglycemia (<54 mg/dL [3.0 mmol/L] or severe) during the treatment phase up to Week 52 (assuming event rates of 3.37 [SD = 7.13] and 4.87 [SD = 7.13] events per participant per year for LY3209590 and insulin degludec, respectively) using a negative binomial distribution α of 0.05.

6. Supporting Documentation

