6.11. Appendix 11: Empirical Estimation of Relative Event Rate

Traditionally, the Poisson distribution has been assumed to draw inference for the rate of rare events. When the event is rare and the sample size is large, it is known that the overall number of events is approximately from Poisson distribution. However, for some not very rare events such as severe hypoglycemic events in T1D participants, the total number of events may not be distributed from Poisson and may be over-dispersed. Assuming Poisson distribution may significantly underestimate the variance, and therefore may reduce the coverage probability and inflate the type 1 error. An empirical method in estimating the variance of the relative event rate without assuming any distribution on the number of events will be provided in this appendix.

Let X_{ij} denote the count response variable for participant j in treatment group i . Let $Y_i = \sum_j X_{ij}$ be the total number of events for treatment group i , and T_i denote the exposure for treatment group i . Let $i = 0$ for the control group and $i = 1$ for the experimental treatment group. The event rate for treatment group i can be calculated as

$$\hat{r}_i = \frac{Y_i}{T_i}$$

The empirical variance of \hat{r}_i is

$$\widehat{Var}(\hat{r}_i) = T_i^{-2} \widehat{Var}(Y_i) = T_i^{-2} n_i S_i^2,$$

where S_i^2 is the variance of X_{ij} for treatment group i . Using the delta-method, the variance of $\log(\hat{r}_i)$ can be estimated as

$$\widehat{Var}(\log(\hat{r}_i)) = Y_i^{-2} n_i S_i^2$$

The relative rate of the experimental treatment versus the control treatment is estimated as

$$\hat{\lambda} = \frac{\hat{r}_1}{\hat{r}_0}$$

The variances of $\hat{\lambda}$ and $\log(\hat{\lambda})$ are

$$\widehat{Var}(\hat{\lambda}) = \hat{\lambda}^2 \widehat{Var}(\log(\hat{\lambda}))$$

$$\widehat{Var}(\log(\hat{\lambda})) = \widehat{Var}(\log(\hat{r}_0)) + \widehat{Var}(\log(\hat{r}_1)) = Y_0^{-2} n_0 S_0^2 + Y_1^{-2} n_1 S_1^2$$

Assuming $\log(\hat{\lambda})$ is asymptotically from a normal distribution, the $100(1 - \alpha)\%$ confidence interval for $\log(\hat{\lambda})$ can be constructed as

$$\left[\log(\hat{\lambda}) - z_{1-\frac{\alpha}{2}} \sqrt{\widehat{Var}(\log(\hat{\lambda}))}, \log(\hat{\lambda}) + z_{1-\frac{\alpha}{2}} \sqrt{\widehat{Var}(\log(\hat{\lambda}))} \right]$$

Then, the $100(1 - \alpha)\%$ confidence interval for $\hat{\lambda}$ is

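### The Level 3 (severe) hypoglycemia rows of SAP 4.6.3.1.1 name no method that works when one arm has no events

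*SAP*

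**What the plan says.** SAP 4.6.3.1.1 plans two comparisons of Level 3 events, each for baseline, Weeks 0-26, 0-52 and 26-52, and the posttreatment period.

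- **Event rate.** The first choice is "Negative binomial regression with treatment and baseline HbA1c, and baseline Level 3 hypoglycemia rate as covariates". For sparse data the row continues: "If the number of events is too small to run the negative binomial regression, the exposure-adjusted rate" will be provided, and the arms will be compared by an empirical method. The row refers the reader to Appendix 10 (Section 6.10), which holds laboratory abnormality limits. The method is in Appendix 11 (Section 6.11), which derives a relative rate and its log-scale variance: "Using the delta-method, the variance of" the log rate is taken from the event total and the between-participant variance in each arm.
- **Incidence.** "Logistic regression with treatment and baseline HbA1c as covariates". The row names no alternative for sparse data.

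Neither row covers an arm with no events or says whether p-values are Wald or likelihood-ratio. SAP 4.6 makes Fisher's exact test, with a risk difference and 95% CI, the default for safety percentages unless otherwise noted. The Level 3 incidence row notes otherwise.

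**The concern.** Severe hypoglycemia is the first safety topic of special interest in SAP 4.6.2.1, and the Level 3 rows are its only planned comparison by period. Some of those periods are short. For a participant who completes treatment, the posttreatment period is about five weeks (Week 52 to Week 57). Protocol 6.6.1 says of that transition, after LY3209590, that "a slow up-titration of the non-study daily basal insulin is necessary to prevent hypoglycemia due to overlapping insulin action". Events falling in one arm only is therefore a pattern these rows should be able to describe.

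If an arm is empty, the rate comparison cannot be calculated and the incidence p-value depends on a software default. Any method chosen at that point would be chosen with the data in view.

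**Working it through.** The documents state no Level 3 count, rate or power, so there is no planned figure to reproduce. The 6 v 0 split below is an illustration.

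**Inputs.** "Approximately 670 participants will be randomized to LY3209590 and insulin degludec in a 1:1 ratio", so 335 per arm. The Week 26 completer figure of 284 per arm (SAP Section 5) was tried as well. Tests are two-sided at 0.05 (Protocol 9.3.1).

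**1. Rate fallback.** Appendix 11 gives Var(log λ) = n₀S₀²/Y₀² + n₁S₁²/Y₁², where Y is an arm's event total and S² the variance of its participant counts. At 6 v 0 the empty arm has Y = 0 and S² = 0, so its term is 335 × 0/0². The relative rate is infinite (or zero, with the arms reversed). No interval or p-value exists.

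**2. Printed p-value.** The last formula in Appendix 11 is p = 2Φ(|log λ|/SE). Its argument is never negative, so p is never below 1. Take 6 v 1, one event per affected participant, 335 per arm with equal exposure:

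- S₁² = (6 − 36/335)/334 = 0.01764, giving a term of 335 × 0.01764/36 = 0.164.
- S₀² = (1 − 1/335)/334 = 0.002985, giving a term of 335 × 0.002985/1 = 1.000.
- SE = √1.164 = 1.079 and z = log 6/1.079 = 1.66.
- As printed, p = 2Φ(1.66) = 1.90. With the minus sign, p = 2Φ(−1.66) = 0.097.

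**3. Incidence at 6 v 0.** Logistic fits used treatment and a simulated baseline HbA1c.

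| Method | p |
|---|---|
| Logistic, Wald, tight convergence | 0.993 to 0.995 |
| Logistic, Wald, looser convergence | 0.87 to 0.91 |
| Logistic, likelihood-ratio | about 0.004 |
| Firth-penalised logistic | about 0.013 (odds ratio about 13) |
| Fisher's exact | 0.031 (335 per arm), 0.030 (284 per arm) |

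- Fisher at 335 per arm: 2 × C(335,6)/C(670,6) = 2 × 0.01528 = 0.031.
- Likelihood-ratio without HbA1c: 2 × [6 log 2 + 329 log(0.98209/0.99104) − 335 log(0.99104)] = 8.37 on 1 df, p = 0.0038.
- The Wald p hardly responds to the data: with tight convergence it is still about 0.99 at 40 v 0.
- The first-line negative binomial model behaves the same way at 6 v 0: Wald p about 0.998 to 0.999, likelihood-ratio p 0.004 to 0.005.
- Fisher at 5 v 0 is 0.061 to 0.062, so 6 v 0 is the smallest empty-arm split below 0.05.

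**4. Chance of an empty arm, posttreatment.** Assume equal Poisson rates and 300 completers per arm followed for 35 days: 300 × 35/365.25 = 28.7 participant-years. P(at least one empty arm) = 1 − (1 − e^(−λ))², with λ = rate × participant-years. SAP 4.1 also counts early discontinuers' time after treatment. If the other 35 per arm average 26 weeks (an assumption), they add 35 × 182/365.25 = 17.4, making 46.2.

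| Assumed severe rate per 100 participant-years | 28.7 participant-years | 46.2 participant-years |
|---|---|---|
| 2 | 81% | 64% |
| 5 | 42% | 19% |
| 10 | 11% | 2% |
| 15 | 3% | 0.2% |

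Most of these are splits no test could detect: Fisher p is 1 at 1 v 0 and about 0.50 at 2 v 0. Under the same equal-rate model at 28.7 participant-years, the chance of an empty arm facing six or more events, 2e^(−λ)P(X ≥ 6), is under 0.01%, 0.2%, 0.8% and 0.7% at the four rates. A real treatment difference would raise it.

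For Weeks 0-26 and 26-52 the chance of an empty arm is about 10% at 2 per 100 and under 1% at 5 or more. For Weeks 0-52 it is negligible.

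**The case against.** A reader might infer that a clear imbalance in severe events would be reported as no difference. The documents do not support that, for three reasons.

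- The rate fallback would return a non-estimable comparison, not a null one, and the exposure-adjusted rates are still to be reported.
- Severe events must be recorded as serious. They therefore enter the SAE tables and the severe hypoglycemia summary by preferred term (SAP 4.6.2 and 4.6.2.1.1), where Fisher's exact test is the default. At 6 v 0 that gives about 0.03.
- A p-value near 1 presupposes a Wald test, which the SAP does not specify.

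A reader might also say the fallback fails in the very case it was written for. That goes too far. SAP 4.1 triggers it on small counts with convergence problems, and Appendix 11 is aimed at over-dispersed events that it describes as not very rare. For low but non-zero counts the variance formula is defined. An empty arm is an edge case.

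Finally, Level 3 rate and incidence are tertiary endpoints outside the multiplicity scheme, so no confirmatory claim rests on them.

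All of this stands and limits the point. It does not remove it. The SAE and preferred-term tables cover the whole safety period including follow-up, and may split events across terms, so they do not replace comparisons by analysis period. SAP 4.1 and Protocol 9.3.5 mention Fisher's exact test beside logistic regression in general terms, but this row selects logistic regression and gives no rule for leaving it.

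**Conclusion.** The point holds as a cheap improvement. With an empty arm, the Level 3 rate fallback is undefined. The incidence model gives an unusable odds ratio and Wald interval, and a p-value between about 0.004 and nearly 1 at 6 v 0 depending on an unstated choice of test. These results follow from the SAP's own formulas and model.

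How often it would matter is uncertain, because the documents give no severe event rate. It is most plausible in the baseline and posttreatment periods, and most empty-arm splits would be too small for any method to detect. The 6 v 0 example is only just below 0.05 on an exact test and should not be read as a likely or a striking result.

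The wrong appendix reference and the missing minus sign are separate errors in the same text. The sign error affects every use of the fallback, not just empty arms, if it is programmed as printed.

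**What to change.** Amend the Level 3 rows of SAP 4.6.3.1.1 and Appendix 11:

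- **Incidence.** Use Firth-penalised logistic regression with a profile-likelihood CI. Alternatively, when an arm has no events, revert to the Section 4.6 default: Fisher's exact test, with an exact CI for the risk difference. State the test type for the regression p-values.
- **Rate.** When an arm has no events, report the difference in exposure-adjusted rates with a permutation test that reassigns whole participants, each with their events and exposure. This is defined at zero and respects the over-dispersion that concerns Appendix 11.
- **Corrections.** Point the fallback to Appendix 11 (Section 6.11), and print the p-value as 2Φ(−|log λ|/SE).

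The cost is a few sentences and some programming, with no new data. The one drawback is that, when an arm is empty, the rate comparison is shown as a difference and not as a ratio like the other rows.
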